The inclusion criteria of the participants in the study included (1) intensive care unit confusion assessment scale (CAM-ICU scale) score of 0-2, (2) age 18 years or older, (3) hospitalized in the intensive care unit for at least 24 hours, (4) Glasgow coma scale score of 13-14-15 points, (5) RASS score between -1 and +1, (6) no hearing problems.

Participants with any of these characteristics will be excluded: (1) intensive care unit confusion assessment scale (CAM-ICU scale) score of 6-7, (2) any psychiatric illness or impaired brain function, (3) defined hearing loss, (4) advanced dementia, (5) younger than 18 years of age, (6) RASS score outside the range of -1 to +1, (7) sedative medication, (8) history of surgery or disease around the ear.

Recruitment, randomisation, and blinding

To assign eligible participants to study groups, a computer-assisted simple randomization method will be employed. The randomization process will be performed by a statistical expert other than the researcher and will be forwarded to the researcher. For this, the website "<https://www.random.org/integer-sets>" will be used. This approach aims to minimize selection bias and control for potential confounding variables by ensuring equal probability of assignment to either the intervention or control group.

Study Intervention

The study consists of four stages.

Phase 1: Development of the Structured Orientation Program: Structured orientation training programs will be developed by the researchers for both AI Nurse and Human Nurse interventions based on the literature (Kasapoğlu et al.,2022; Ma et al.,2025). While the AINurse training program will be implemented in the experimental group, the Human Nurse training program will be implemented in the control group. The content of the structured training program for both groups will be the same (Appendix-2). The training content will be sent to the opinion of 10 experts who are experts in intensive care and AI, and changes will be made in the training program.

In the AINurse training program, the training text will be written in a patient-friendly language to enhance comprehensibility. The Narrative Orientation Experience model will be used not only to deliver information but also to support the patient's psychosocial adaptation to the intensive care environment. Within this method, key information such as time, place, care

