Data will be collected using the sociodemographic characteristics form, a clinical patient information form, the Confusion Assessment Method-Intensive Care Unit (CAM-ICU), and the Hospital Anxiety and Depression Scale (HADS). In the initial stage, patients will be screened for the presence of delirium using the CAM-ICU. Following this, their sedation and agitation levels will be assessed using the Richmond Agitation Sedation Scale (RASS), and eligibility for study inclusion will be determined based on these scores. The RASS is a validated tool used to assess the level of sedation and agitation in patients admitted to intensive care units, with scores ranging from +4 to -5. Positive scores indicate increasing levels of agitation (e.g., +4: combative, +3: very agitated, +1: restless), while negative scores reflect deeper levels of sedation (e.g., -1: drowsy, -2: lightly sedated, -5:unarousable). A score of 0 indicates an alert and calm state (Sessler et al., 2002).

Sociodemographic information form: The sociodemographic information form developed by the researchers consisted of eight questions about name, age, gender, occupation, marital status, education, smoking, and alcohol use. (Appendix-1)

Clinical patient information form: It was created by the researchers from a total of 11 questions, including the patient's diagnosis, acute physiological and chronic health evaluation II (APACHE II) score, mean arterial pressure (MAP), blood urea nitrogen (BUN), metabolic

acidosis, use of analgesic drugs, use of physical restraint, infection, respiratory failure and corticosteroid use, and the presence of catheters/tubes in the patient. (Appendix-1)

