Data collection will take place between July 2025 and July 2026. After obtaining written informed consent, randomization will be performed among patients hospitalized in the intensive care unit and the cardiovascular surgery intensive care unit who meet the inclusion criteria and voluntarily agree to participate in the study. In the first stage, patients' CAM-ICU form and RASS scores will be calculated. For patients who meet the inclusion criteria, the

sociodemographic characteristics form and clinical patient information form will be completed by the researchers. Patients in the intervention group included in the study will be given structured AI-Nurse orientation training starting at 10:00 am (approximately 10 minutes), and then the patient will listen to the daily morning news on television. At the end of the day, at 16:00, CAM-ICU and HADS will be evaluated. This process will continue with the same patient for three days. If the delirium score is between 3 and 7 points for three days and the RASS value is +4 belligerent, +3 very agitated, -2 slightly sedated, -3 moderately sedated, -4 deep sedation, -5 unstimulated, this training and follow-up process will be stopped, and the intervention will be ended. Patients assigned to the control group will fill in the same forms, and after the structured orientation training is given by the researcher (Human Nurse), the television will be turned on in the same way, and the daily news will be listened to. At the end of the day, CAM-ICU and HADS will be evaluated at 16:00. This practice will continue with the same patients for three days. After three days of follow-up, the length of stay of the patients in the intensive care unit will be monitored until discharge.

Data Analysis

Data will be analyzed using IBM SPSS Statistics, Version 28.0 (Armonk, NY: IBM Corp., 2021). Sociodemographic characteristics will be reported using descriptive statistics such as frequency, percentage, mean, and standard deviation. Descriptive statistics will be used to analyze the data. Whether the data are normally distributed will be evaluated with the Shapiro-Wilk test. The t-test will be used for normally distributed data. If the data are not normally distributed, the Mann-Whitney U test will be used.

Ethical Consideration

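### Age, APACHE II and ICU type are known for each patient, but the named tests cannot use them: a valid analysis that gives up some precision for H1 and H3

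*Protocol*

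**What the plan says.** **Covariates.** Under Data Collection Instruments, the sociodemographic form "consisted of eight questions about name, age, gender, occupation, marital status, education, smoking, and alcohol use". The clinical patient information form includes the "acute physiological and chronic health evaluation II (APACHE II) score".

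**Timing.** Data Collection and Follow-up says that, for eligible patients, the "sociodemographic characteristics form and clinical patient information form will be completed by the researchers". This comes after the sentence on randomisation and before the account of the first 10:00 session. No scoring window for APACHE II is given.

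**Allocation.** Under Recruitment, randomisation, and blinding, "a computer-assisted simple randomization method will be employed". No stratification by severity, age or unit is mentioned. The section adds: "This approach aims to minimize selection bias and control for potential confounding variables by ensuring equal probability of assignment". Patients come from the general ICU and the cardiovascular surgery ICU; the latter accounts for 450 of the 1950 stated annual admissions.

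**Analysis.** Data Analysis says: "Sociodemographic characteristics will be reported using descriptive statistics such as frequency, percentage, mean, and standard deviation". After a Shapiro-Wilk check, "The t-test will be used for normally distributed data", and "If the data are not normally distributed, the Mann-Whitney U test will be used". No covariate or regression model is named, no use of APACHE II is stated, and no test is tied to H1 or H3 individually.

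**The concern.** Severity, age and type of unit plausibly predict ICU stay, and perhaps delirium. A two-sample test leaves whatever variation they explain in the error term, so a trial of given size has less power than its own data could provide. Simple randomisation balances these variables on average but not necessarily in the one allocation that occurs. Mixing general and cardiovascular surgery patients makes the case mix more varied.

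The timing also matters. If adjustment is left open until the baseline table is seen, the decision to adjust, and the choice of variables, can follow the data. Naming the covariates beforehand prevents that. The sample size has not yet been set, so the change can be made at little cost.

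**Working it through.** **1. Inputs.** The protocol states no sample size, alpha, power, effect size or standard deviation; the sample size is to follow a pilot in 10 patients. There is therefore no figure to reproduce. Assumed here: two-sided alpha 5%, 80% unadjusted power, equal arms, and R², the share of outcome variance that the covariates explain jointly, over a range.

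**2. Power.** Adjustment multiplies the residual SD by √(1−R²). With 1.96 + 0.84 = 2.80 for 80% power, adjusted power is Φ(2.80/√(1−R²) − 1.96). The gain is equivalent to multiplying the sample size by 1/(1−R²).

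| R² | 2.80/√(1−R²) | Power | Equivalent extra patients |
|---|---|---|---|
| 0.02 | 2.83 | 81% | 2% |
| 0.05 | 2.87 | 82% | 5% |
| 0.10 | 2.95 | 84% | 11% |
| 0.25 | 3.23 | 90% | 33% |

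**3. The same in patients.** For an illustrative standardised difference of 0.5, n per arm = 2 × 2.80²/0.5² = 62.7, so 63. Multiplying by (1−R²) gives 62, 60, 57 and 48 per arm for the four rows.

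**4. Is the unadjusted test valid?** In a simulation with a normal outcome and one covariate (30 or 64 per arm, R² 0.05 to 0.30, 4000 runs per setting), rejection under the null was 0.043 to 0.060 unadjusted and 0.048 to 0.054 adjusted. Both scatter around 5%. With 64 per arm and a difference of 0.5 SD, power was 0.80 unadjusted, against 0.82 (R² 0.05), 0.84 (0.10), 0.87 (0.20) and 0.91 (0.30) adjusted, in line with step 2.

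**5. Chance imbalance.** The standardised difference between arms in one covariate has standard error 2/√N. For N = 60 this is 0.258, and the chance of an imbalance of at least 0.3 SD is 0.245. For N = 100 it is 0.20 and the chance is 0.134; for N = 200 it is 0.141 and the chance is 0.034. A 0.3 SD imbalance moves the unadjusted difference by 0.3 × √R² outcome SDs: 0.04 at R² = 0.02, 0.09 at 0.10 and 0.16 at 0.30.

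**6. Where in the range?** H1 concerns delirium-free days. Delirium is followed for three days in patients who enter with a CAM-ICU score of 0–2, a Glasgow score of 13–15 and RASS between −1 and +1. The outcome is thus apparently a count of 0 to 3 with a ceiling, over a narrowed range of severity, so a low R² is quite possible. ICU stay (H3) is followed to discharge without such a ceiling, so it is the likelier beneficiary. This is a judgement; the documents hold no data on it.

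**The case against.** **Adjustment is normally specified in the SAP.** That is often so, and the SAP is not at hand. But the protocol does not leave the method open: it names tests that cannot take a covariate. If an SAP adds adjustment, the two documents would need to be aligned. What stands is that Data Analysis does not forbid a further model, and its tests are not assigned to H1 or H3 one by one.

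**Nothing is wrong with a t-test or Mann-Whitney test after randomisation.** This stands. The statement that randomisation aims to control confounding is also true in expectation.

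**A reader might infer that the planned test is biased or has an inflated false-positive rate.** The protocol does not support that. Given a 0.4 SD imbalance in a covariate with correlation 0.4 to the outcome, the unadjusted test would reject a true null about 7% of the time at N = 60 and 10% at N = 100. But an imbalance that large or larger occurs in only about 12% and 4.6% of such trials. With balanced arms the same test rejects less often than 5%, and the overall rate stays near 5%. The two sample sizes and the correlation are assumptions too.

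**The gain may be trivial.** For H1 this is a fair point: at R² of 0.02 to 0.05, power rises by only one or two percentage points. The formula also rests on normal theory, so the gains do not carry over exactly where the Mann-Whitney test would have been used.

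**The values may not be true baseline values.** That they precede the first session is inferred from the order of the text, which also places form completion after randomisation. This stands, and the fix must deal with it.

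**Conclusion.** The point holds as a low-cost improvement in efficiency, not as an error. The protocol records age and APACHE II, recruits from two different units without stratification, and names only tests that cannot use this information. The loss is negligible if the covariates explain about 2% of outcome variance and material at 20% or more. It is more likely to matter for H3 than for H1.

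The size rests on assumed R², two-sided 5% alpha, 80% unadjusted power and approximately normal theory. That age, APACHE II and unit predict these outcomes is plausible but is not documented in the protocol.

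**What to change.** In Data Analysis, state that H1 and H3 are each compared with one pre-specified regression model containing arm, age, APACHE II and ICU type (general or cardiovascular surgery), and no other covariates:

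- **H1:** a linear model of delirium-free days with robust standard errors, because the outcome is bounded and unlikely to be normal.
- **H3:** a linear model of log ICU stay.

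Use only covariate values that refer to the period before the first session, and state the APACHE II scoring window in Data Collection and Follow-up. Report the t-test or Mann-Whitney comparison as sensitivity analysis. If chance imbalance is discussed as a reason for the change, say alongside that the overall type I error of the unadjusted test is about 5%.

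The cost is analysis wording and a decision on when APACHE II is scored. Age and APACHE II are already on the forms, the unit is known for every patient, and SPSS fits both models.

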RESEARCH PROTOCOL

Official Title: Effects of AINurse Orientation Program on Psychological Outcomes and Length of Hospital Stay: A Randomized Controlled Trial

Date of the document: September 1, 2025

Method

Aim

This study aimed to develop a structured AINurse and Human Nurse orientation training program for intensive care unit (ICU) patients and compare the effects of these training programs on ICU patients' delirium-free days, level of anxiety and depression, and length of stay in the ICU.

Study Type and Design

This study is designed as a single-center, randomized controlled experimental study. The study trial protocol will be registered on clinicaltrials.gov . The Consolidated Standards of Reporting Trials (CONSORT) diagram will be used for reporting the study.

Hypotheses of the Study

H1: Patients who receive the structured AINurse patient orientation training program will have longer delirium-free days than patients who receive Human Nurse orientation training.

H2: Patients who receive the structured AINurse patient orientation training program will have lower levels of anxiety and depression than patients who receive the Human Nurse orientation training.

H3: Patients who receive the structured AINurse patient orientation training program will have shorter lengths of stay in the intensive care unit than patients who receive the Human Nurse orientation training.

Setting, Participants, and Sample Size

The study is planned to be conducted between July 2025 and July 2026 in the adult intensive care unit of Koç University Hospital, a tertiary care hospital in Türkiye. The general intensive care unit (GICU) of Koç University Hospital has 16 beds and the cardiovascular surgery intensive care unit (CVSICU) has eight beds. The hospital where the study will be conducted has a total of 1950 patient admissions annually, 1500 in the NICU, and 450 adult patients in the CVSICU. While the experimental group will receive the AI Nurse Orientation Training Program, the control group will receive the Human Nurse Orientation Training Program. Since there is no similar study to this study, a pilot study will be conducted with 10 patients. After the pilot study, the sample size will be calculated using G-Power.

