Phase 4: Implementation of structured orientation training to intervention and experimental group: In the experimental group, the structured AI-Nurse orientation program will be listened to twice daily (10:00 and 14:00) through a headset connected to a structured

audio recording application. The content will include orientation to time and environment but will exclude any personally identifiable information such as the patient's name. Following each orientation session, the daily news will be played with the help of the television in the patient's room (at 10:30-14:30), aiming to enhance environmental awareness and perception of real-time audio streaming. The TTS engines to be used will be able to provide real-time audio streaming. This intervention will be implemented by the same researcher over a three-day period. Anxiety and depression levels, as well as the CAM-ICU score, will be assessed both before and after the intervention. After three days of structured AI-Nurse training, the patient's discharge time from the ICU will be followed and recorded. In the control group, the structured orientation training will be given face-to-face by the Human-Nurse researcher. The patient in this group will also be monitored for signs and symptoms of delirium for three days. Anxiety and depression levels will be measured prior to the intervention, while post-intervention evaluations will include the number of delirium-free days, anxiety and depression scores, and length of stay in the ICU.

Data Collection Instruments

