Confusion Assessment Method for the Intensive Care Unit (CAM-ICU): This form will be utilized to assess the presence of delirium in critically ill patients. Originally developed by Ely et al. (2001) to facilitate the identification of delirium by nurses and physicians in intensive care settings, the Turkish validity and reliability of the scale were established by Akıncı et al. (2005), with a reported Cronbach's alpha coefficient of 0.96, indicating excellent internal consistency. The CAM-ICU evaluates four key features in critically ill patients: (1) acute onset or fluctuating course of mental status, (2) inattention, (3) altered level of consciousness, and (4) disorganized thinking. A positive diagnosis of delirium is made when the first two criteria are present, along with either the third or fourth. The scale yields a total score ranging from 0 to 7, with interpretive cut-off points as follows: 0–2 indicating no delirium, 3–5 suggesting mild to moderate delirium, and 6–7 indicating severe delirium (Akıncı ve ark.,2005). (Appendix-1)

The Hospital Anxiety and Depression Scale (HADS): This scale was developed by Zigmond and Snaith (1983) to assess the severity and risk of anxiety and depression in hospitalized patients. The Turkish validity and reliability study of the scale was conducted by Aydemir et al. (1997), reporting a Cronbach's alpha coefficient of 0.85, inter-item correlation coefficients ranging between 0.81 and 0.85, and a split-half reliability coefficient of 0.85, indicating strong internal consistency. The scale comprises 14 items in a 4-point Likert format. Odd-numbered items assess anxiety symptoms, while even-numbered items assess depressive symptoms. Items 1, 3, 5, 6, 8, 10, 11, and 13 are reverse scored (3, 2, 1, 0), while items 2, 4, 7, 9, 12, and 14 are scored progressively (0, 1, 2, 3). Subscale scores are obtained by summing the relevant items: questions 1, 3, 5, 7, 9, 11, and 13 for the anxiety subscale (HAD-A), and questions 2, 4, 6, 8, 10, 12, and 14 for the depression subscale (HAD-D). In the Turkish adaptation, the cut-off scores were identified as 10/11 for the anxiety subscale and 7/8 for the depression subscale. Scores exceeding these thresholds indicate a risk of clinically significant anxiety or depression (Yiğitoğlu et al., 2021). (Appendix-1)

Data Collection and Follow-up

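### The protocol describes HADS timing in two ways, and H2 fixes no day, summary or use of baseline for tests that take one value per patient

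*Protocol*

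**What the plan says.** - **Daily schedule (Data Collection and Follow-up).** For the AI-Nurse arm, at 16:00: "CAM-ICU and HADS will be evaluated. This process will continue with the same patient for three days". The Human Nurse arm has the same 16:00 assessment, and "This practice will continue with the same patients for three days". The steps listed before training starts are CAM-ICU, RASS and the sociodemographic and clinical forms. HADS is not among them.
- **Before/after schedule (Study Intervention, Phase 4).** For the AI-Nurse arm: "Anxiety and depression levels, as well as the CAM-ICU score, will be assessed both before and after the intervention". For the control arm: "Anxiety and depression levels will be measured prior to the intervention, while post-intervention evaluations will include the number of delirium-free days", followed by anxiety and depression scores and ICU stay. No day is attached to the later reading, and no daily HADS is mentioned.
- **Hypothesis H2.** Patients in the AI-Nurse arm "will have lower levels of anxiety and depression than patients who receive the Human Nurse orientation training". No day, change score or per-patient summary is named.
- **Outcomes under H2.** HADS gives two subscales (Data Collection Instruments): "Odd-numbered items assess anxiety symptoms, while even-numbered items assess depressive symptoms".
- **Analysis (Data Analysis).** After a Shapiro-Wilk check: "The t-test will be used for normally distributed data. If the data are not normally distributed, the Mann-Whitney U test will be used". No other inferential method appears.

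**The concern.** One section yields up to three correlated HADS readings per patient and no baseline; another yields one baseline and one later reading. H2 compares arms, and a two-sample test needs a single number for each patient. The protocol does not say whether that number is the day-3 score, a three-day mean, a change from baseline or something else, so the choice could be made after the data are seen.

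The simplest choice, a plain day-3 comparison, keeps its error rate if the day is named in advance. It has three costs: the baseline that Phase 4 requires goes unused, the day-1 and day-2 readings go unused, and patients without a day-3 reading are left out. If HADS stops at ICU discharge, which the protocol does not settle, that last loss could be related to ICU stay, the outcome of H3.

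The sample size is still to be calculated after the pilot, and any calculation for H2 needs to know which HADS value is compared.

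**Working it through.** The protocol gives no sample size, alpha, SD or correlation for HADS, so there is no stated figure to reproduce. The figures below assume two-sided alpha 0.05, all three readings present for each patient, and the same correlation r between any two days, with r from 0.5 to 0.8.

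**1. The two schedules side by side**

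| | Data Collection and Follow-up | Phase 4 |
|---|---|---|
| HADS before the programme | not listed | required in both arms |
| HADS on days 1 and 2 | 16:00 each day | not mentioned |
| HADS at the end | 16:00 on day 3 | after the programme, no day named |

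The two agree only if the Phase 4 baseline is added to the daily schedule and its later reading is taken as the day-3 value. The protocol does not say so.

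**2. If patient-days were pooled as independent**

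The variance of an arm difference is understated by the factor 1 + 2r. The true error of a nominal 5% test is 2 × (1 − Φ(1.96/√(1 + 2r))).

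- r = 0.5: factor 2.0, error 0.166
- r = 0.7: factor 2.4, error 0.206
- r = 0.8: factor 2.6, error 0.224

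**3. If each subscale were tested on each day**

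There would be 2 × 3 = 6 tests. If independent, the chance of at least one false positive is 1 − 0.95⁶ = 0.265. With correlated test statistics (simulated, 500,000 draws, between-subscale correlation assumed 0.6) it is 0.212 at r = 0.5, 0.185 at r = 0.7 and 0.167 at r = 0.8.

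**4. If one pre-named day is used**

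The error rate stays at 5% per subscale; the cost is precision. With complete data and a baseline that correlates r with day 3, adjustment multiplies the day-3 variance by 1 − r².

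- r = 0.5: 1 − 0.25 = 0.75, a cut of 25%
- r = 0.7: 1 − 0.49 = 0.51, a cut of 49%

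**5. Day 3 or the three-day mean as the contrast**

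The variance of a three-day mean relative to one day is (1 + 2r)/3: 0.67 at r = 0.5 and 0.80 at r = 0.7. If the effect is the same every day, the mean is more precise. If it grows, say −1, −1.5, −2 (assumed), squared signal to noise with complete data is proportional to 2² = 4 for day 3. For the mean it is 1.5²/0.80 = 2.81 at r = 0.7 and 1.5²/0.667 = 3.38 at r = 0.5. The mean would then need 4/2.81 = 1.42 or 4/3.38 = 1.19 times as many patients. Neither contrast is better in every scenario.

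**The case against.** The best defence is that Phase 4 already points to one later value per patient, for which a two-sample test is valid, and that the model for repeated readings may sit in a statistical analysis plan that is not at hand. The first half stands: a t-test or Mann-Whitney U test on a pre-named day-3 score, three-day mean or change score would hold its error rate. The second half does not clear the point. The disagreement over when HADS is read lies within the protocol, and the protocol has its own Data Analysis section that commits to tests without saying what they are applied to.

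Three stronger readings are tempting and are not supported:

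- A reader might infer that H2 must end in pooled patient-days, six separate tests or a single discarded-data day. That list is not exhaustive, since a per-patient summary is also open, and the protocol announces neither pooling nor day-by-day testing.
- A reader might infer that a day-3 analysis will lose a large share of patients. The protocol gives no figure for how many leave the ICU within three days. It tracks discharge after the three days, which suggests that patients are expected to stay. A precision gain that rests on an assumed departure rate has no source here.
- A reader might infer that a three-day average is the right primary contrast. Step 5 of the working shows that this depends on how the effect develops.

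**Conclusion.** The point holds as a gap in definition with a better method available on data already planned. The two HADS schedules do not match, the daily one omits the baseline that Phase 4 requires, and H2 fixes no day, summary or use of baseline.

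The error figures are conditional on uses that the protocol does not state: about 17-22% under pooling (assumed r 0.5-0.8) and about 17-21% over six tests (assumed between-day correlation 0.8-0.5, between-subscale 0.6), or 26% if independent. They show why the choice should be fixed, not what the trial will do. The 25-49% cut in day-3 variance assumes complete data and a baseline correlation of 0.5-0.7. Selection on ICU stay is a possibility only, and depends on whether HADS ends at ICU discharge.

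**What to change.** 1. Reconcile Phase 4 with Data Collection and Follow-up: state one HADS schedule for both arms, including the pre-intervention reading, and say whether readings continue after ICU discharge within the three days.
2. For H2, name one repeated-measures mixed model per subscale, with arm, day, arm-by-day, baseline HADS as covariate and unstructured covariance. Use all 16:00 readings and keep patients with fewer than three.
3. Name one contrast per subscale in advance. The baseline-adjusted day-3 difference fits the Phase 4 wording best, with the three-day average as supportive; the reverse is open to the sponsor. Say how the two subscale results together decide H2.
4. Base any H2 sample-size calculation on that contrast, and present any precision gain as dependent on the scenario.

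The cost is a few sentences and slightly more analysis work in SPSS, which the protocol already names. The model brings an assumption about missing readings that should be stated. The only reading beyond the daily schedule is the baseline, which Phase 4 already requires.

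### The delirium stop rule either stops no training or, read loosely, ends outcome scoring because of the outcome, and only the AI-arm text states it

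*Protocol*

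**What the plan says.** The stop rule is in the protocol, Data Collection and Follow-up. Its condition is "If the delirium score is between 3 and 7 points for three days and the RASS value is +4 belligerent, +3 very agitated", and the RASS list then continues with -2, -3, -4 and -5. Its consequence is "this training and follow-up process will be stopped, and the intervention will be ended".

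In the same paragraph, the AI-arm day consists of orientation training, television news, and then scoring: "At the end of the day, at 16:00, CAM-ICU and HADS will be evaluated". The next sentence is "This process will continue with the same patient for three days", and the stop rule follows directly.

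The control-arm description comes after the rule. It has the same 16:00 scoring, says "This practice will continue with the same patients for three days", and mentions no stopping. Study Intervention, Phase 4 likewise has controls monitored for delirium over three days, with no stop rule. The paragraph ends with "After three days of follow-up, the length of stay of the patients in the intensive care unit will be monitored until discharge".

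On timing, Phase 4 says the AI programme "will be listened to twice daily (10:00 and 14:00"), over three days. Phase 4 also calls for anxiety, depression and CAM-ICU measurements before and after the intervention.

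**The concern.** A stop rule in a three-day intervention should be able to act within the three days, and it should not switch off outcome measurement in the patients whose outcome is poor. This one has trouble on both counts.

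Its delirium range, 3 to 7, is the whole range that Data Collection Instruments classes as delirium, and H1 compares delirium-free days. If meeting the rule ends daily scoring, whether an outcome is observed depends on the outcome itself. If the rule operates in one arm only, that dependence differs between arms, and randomisation does not protect against it. HADS, the measure for H2, is taken at the same 16:00 assessment and would end with it.

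**Working it through.** The protocol gives no figure to reproduce here. The check is a timeline, followed by one illustration.

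**Inputs**
- Entry CAM-ICU is 0-2 (inclusion criteria), so baseline cannot count as a day at 3-7.
- AI sessions are at 10:00 and 14:00 on three days (Study Intervention, Phases 2 and 4): 2 × 3 = 6, the last at 14:00 on day 3.
- CAM-ICU and HADS are scored at 16:00 each day (Data Collection and Follow-up): 3 of each.

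**Literal reading: a score of 3-7 on all three days, plus a listed RASS value**
- The third qualifying score is available at 16:00 on day 3 at the earliest.
- Sessions left: 6 − 6 = 0. Daily scores left: 3 − 3 = 0 of each.
- The rule stops no training. With follow-up taken as the three-day routine, no data are lost.

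**Any-day reading: one qualifying day is enough**

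| Trigger at 16:00 on | Sessions stopped | CAM-ICU scores ended | HADS scores ended |
|---|---|---|---|
| Day 1 | 6 − 2 = 4 | up to 3 − 1 = 2 | up to 2 |
| Day 2 | 6 − 4 = 2 | up to 3 − 2 = 1 | up to 1 |
| Day 3 | 6 − 6 = 0 | 0 | 0 |

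Data Collection and Follow-up names only the 10:00 session. Counting one session a day, 2 of 3 are stopped on day 1 and 1 of 3 on day 2; the score counts do not change.

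Scoring ends on this reading because the rule stops training and follow-up as one unit. It directly follows a sentence whose daily process includes the 16:00 CAM-ICU and HADS, and the paragraph later uses follow-up for the same three days. The counts are upper bounds, because some patients who meet the rule, for example at RASS -5, could not be assessed anyway.

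**RASS**
- RASS is scheduled at screening. The 16:00 assessment names only CAM-ICU and HADS, so the RASS half of the rule has no stated daily measurement.
- Of 10 levels (-5 to +4), 3 are in the entry range and 6 in the stop list. 10 − 3 − 6 = 1 is in neither: +2. This is minor.

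**Direction if the rule ran in the AI arm only (illustration with assumed rates)**

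Assume no treatment effect, a 20% chance of delirium on each day independently, and a listed RASS value on every delirious day.
- Fully scored arm: 3 × 0.8 = 2.400 mean delirium-free days.
- Stopped arm, unscored days counted as not delirium-free: 0.8 + 0.64 + 0.512 = 1.952, a shift of −0.448.
- Stopped arm, unscored days counted as delirium-free: 3 − (1 − 0.512) = 2.512, a shift of +0.112.

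The assumptions were then varied: daily onset 10-30%, next-day delirium equal to onset or 60%, and a listed RASS value on 25-100% of delirious days. The shifts ran from −0.04 to −0.57 and from +0.01 to +0.45 respectively. These show only that the sign is not fixed; they do not estimate the effect in this trial.

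**The case against.** The strongest reply is that this is one badly drafted sentence. On its literal reading it is idle and harmless, and all damage to H1 and H2 needs a non-literal reading of the timing and the view that follow-up includes scoring. This stands in part: the literal reading with narrow follow-up loses nothing, and neither does a day-3 trigger. But a rule that cannot stop any training is unlikely to be what was meant, and the more workable reading is the one that ends scoring.

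For H2, the trigger-day HADS at 16:00 follows the last session given and could serve as the post-intervention score that Phase 4 asks for. That stands, and it is why H2 is less affected than H1. It does not replace the later CAM-ICU days that H1 needs.

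Three stronger readings are tempting, and the documents do not support them:
- A reader might infer that length of stay (H3) is lost too, since Phase 4 says of stopped or completed patients alike only that "discharge time from the ICU will be followed and recorded". That sentence has no link to the stop rule, and Data Collection and Follow-up places length-of-stay monitoring after the three days of follow-up, as a separate step.
- A reader might infer that the rule is meant for the AI arm only. This rests on placement alone. The control text is an abbreviated parallel description, and the rule may be meant for both arms. The supportable point is that the protocol does not say so.
- A reader might infer a bias in favour of the AI arm. The sign depends on how unscored days are counted, which a statistical analysis plan may settle.

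A statistical analysis plan can set how missing days are handled, but it cannot recover scores that the protocol told staff not to take.

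**Conclusion.** The concern holds in a conditional form, and the rule should be amended. Read literally, it stops 0 of 6 sessions and, with narrow follow-up, costs no data. If any qualifying day was meant, it ends up to 2 (day-1 trigger) or 1 (day-2 trigger) of 3 daily CAM-ICU and HADS scores. That applies only to patients who are delirious and also have RASS +3, +4 or -2 to -5, not to all delirious patients. The loss is outcome-dependent for H1 and, less so, for H2. If the rule is applied as placed, scoring would also differ between arms.

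The conclusion rests on the stated session and scoring times and on reading the follow-up process as including the 16:00 assessments. The protocol does not say how many patients would meet the rule, so the effect on the results cannot be sized. Confidence is medium, because the intended timing and arm coverage are not stated.

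**What to change.** Amend the rule in Data Collection and Follow-up so that:
- it is evaluated at each daily 16:00 assessment, with RASS recorded then;
- it is stated to apply identically in both arms;
- meeting it stops only the remaining training sessions;
- CAM-ICU, and HADS where the patient can answer, continue to day 3, and length-of-stay recording continues to ICU discharge, for all randomised patients;
- RASS +2 is added to the list or its omission justified.

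The clinical threshold remains for the investigators to set. The cost is a short protocol amendment and a daily RASS. The 16:00 CAM-ICU and HADS are already planned in both arms, and the rule already needs a RASS value. The downside is small: some patients receive fewer sessions.
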